### From the Swedish Cardiac Arrest Register the following variables will be collected:

All EMS units participating in TANGO2 report to the SCAR. For all EMS treated OHCA the following variables will be collected from the Swedish Cardiac Arrest Register:

Date of OHCA, Age, Sex, Location of OHCA, CPR prior to EMS arrival, highest medical educational level of CPR provider, first recorded rhythm, defibrillation, airway management and drug administration, Return of spontaneous circulation (ROSC) and survival to admission to hospital.

In calls where there is no matching report in SCAR, ambulance records will be reviewed; if EMS has performed CPR or the patient had been defibrillated by an AED the case will be classified as "EMS treated" and corresponding variables will be extracted from ambulance records instead.

The EMS will obtain information on what type of CPR that was provided to the patient before their arrival at the scene. This information is obtained by observing on-going CPR at their arrival and asking bystanders what type of CPR they provided. EMS crew will also ask bystanders what kind of CPR training they have according to a three-leveled division of the bystander's medical educational level (a – off-duty professional caregiver, doctor, nurse; b – CPR-trained layman (including off-duty police and fire-fighters); or c – layman with no CPR training). This information is a part of SCAR, but there will be emphasis on obtaining this specific data in the TANGO2 trial. Survival is collected for primary endpoint at day 30 from SCAR through linkage with the Swedish public population register (folkbokföringsregistret). For the secondary outcome of neurologically favorable outcome CPC is obtained through SCAR. In a subset of patients (survivors treated at specifically named hospitals), a comprehensive neurological assessment using Patient Reported Outcome Measurement (PROM) related follow-up is performed between 30-90 days. This follow-up is performed by a nurse and/or behavioral therapists blinded to the intervention allocation. This comprehensive follow up will not be possible in all sites of the TANGO2 trial.

## **8.1 Data handling and record keeping**

For each call to the dispatch center a unique log number automatically is generated. This log number is stored at the dispatch center and used to match calls with EMS records, SCAR reports and hospital data. All log numbers and audio-files related to the study will be saved and kept at SOS Alarm, Stockholm. A list with all log numbers will be exported to a study specific database at the center for resuscitation science. A list of all randomized calls with the randomization allocation for each case will be generated by the random sequence constructor and will be exported separately. Finally, data from call audit evaluation, SCAR reports and EMS and hospital records will be imported. All data will be merged and stored in a specific database at center for resuscitation science. This system fulfills all criteria for handling of patient data according to the Swedish legislation on management of personal data "GDPR". In the database, the allocation of each specific case will be blinded during the data collection to avoid any bias in reporting or collecting data. Allocation concealment will be preserved. In the central database there will be manual crosschecking and completion of missing data through EMS and hospital records.

## 9. Ethical considerations

### 9.1 Informed consent

This research group has a longstanding experience to perform studies in cardiac arrest patients, like the present, within the prehospital setting. In OHCA, the victim is unconscious and therefore incapacitated of providing informed consent. OHCA is however also a medical emergency and treatment has to be started immediately, making informed consent by a relative or legally authorized representative impossible due to practical reasons. As stated by the Helsinki declaration 2008, paragraph 30:

“Research involving subjects who are physically or mentally incapable of giving consent, for example, unconscious patients, may be done only if the physical or mental condition that prevents giving informed consent is a necessary characteristic of the research group. In such circumstances the physician must seek informed consent from the legally authorized representative. If no such representative is available and if the research cannot be delayed, the study may proceed without informed consent provided that the specific reasons for involving subjects with a condition that renders them unable to give informed consent have been stated in the research protocol and the study has been approved by a research ethics committee. Consent to remain in the research must be obtained as soon as possible from the subject or a legally authorized representative.”

This study has been approved by the ethics committee of Stockholm; Dnr 2014/97-31/2 and reasons for involving patients unable to give informed consent have been stated in the research plan.

### 9.2 Potential risks

For the individual cardiac arrest patient, rapid actions by bystanders can lead to an increased chance of survival. Unless some form of life-support activity is performed before arrival of the EMS, survival is dismal. CPR itself rarely leads to damage other than rib fractures. Any pain and discomfort after a successful survival is not proportional to the gain of being rescued to life. This pain and discomfort is also relatively simple to treat. During CPR, the patient is unconscious and thus experiences no pain. The risk of injury associated with CPR is insignificant compared to the potential benefits of treatment. Those patients who survive to 30 days after a cardiac arrest often have good quality of life with only minor neurological disability. This contradicts the fear that an increased number of cases of successful resuscitation lead to a large number of surviving patients with severe disabilities. For the helper, however, some discomfort can arise. Potential risks with this trial are delayed start of CPR due to inclusion and randomization. These issues are separately evaluated in the TANGO2 RUN-IN and TANGO2 PILOT study. Performing CPR is associated with great emotional stress. It is important to be prepared for the reactions that can arise among the lay volunteers. Fear of transmission of contagious diseases associated with CPR is greatly exaggerated. Only a few such cases have been reported worldwide. A small but important population of all OHCA are due to respiratory causes,

i.e. drowning, strangulation, hanging or intoxication, some of these involve children. These cases are filtered out at the dispatch center and excluded from the study as described in the study protocol. We believe that a small group of unclear cases that are not identified by either the witness or by the dispatcher at the dispatch center (severe renal failure, pulmonary embolism, hemorrhagic stroke or chronic obstructive pulmonary disease) could experience a small risk with this intervention. These are very few in numbers and already have a very poor prognosis.

### **9.3 Potential benefits**

Survival after OHCA is very poor, in Sweden ranging between 10-12%. Experimental studies and previous randomized trials have shown that successful CPR can be achieved with CO-CPR. Rescue breaths are technically difficult and take time from chest compressions. In non-cardiac causes of OHCA, rescue breathing might be more important. These cases are therefore excluded prior to randomization. CO-CPR could lead to an earlier start of CPR, no interruptions in chest-compressions and could therefore be beneficial for a majority of cases. In cases of OHCA immediate, effective chest compressions is of absolute necessity to increase the otherwise low chance of survival.

Today, Sweden has amongst the highest rates of bystander CPR in Europe making a study like this possible for the first time. An additional simplification of the CPR-algorithm introducing CO-CPR could perhaps increase survival rates in Sweden but has the potential to dramatically increase bystander rates throughout Europe and more.

A simplified method of CPR with shorter CO-CPR courses optimally provided by the Swedish CPR council will be more cost-effective in companies, schools and throughout society and could enhance the care for this patient group nationally and internationally. In summary, whether CO-CPR leads to a survival rate no worse than, equally effective, or even superior to standard CPR in situations where the bystander has previous CPR training remains unclear. This clinical question remains unanswered while millions of people are trained in CPR worldwide each year. The potential benefits of this study are two-fold in the sense that the results can lead to increased survival rates: 1) simplified CPR might be better than traditional CPR b) simplified CPR could lead to more people performing it.

## 10. Data analytic and statistical analysis plan (SAP)

### 10.1 General statistical analysis plan

This trial is designed to investigate whether CO-CPR is no worse than S-CPR using a non-inferiority design. It has also been designed for the possible of a superiority testing. This statistical design has been chosen appropriately judged on the presumption that CO-CPR has potential clinical benefit but also is easier to perform (and therefore would lead to a higher number of patients receiving the treatment). The largest difference in 30-day survival (primary outcome) that is considered clinically relevant is 1.0 percentage point (please see also section 9.3).

Eligibility, allocation, inclusion and exclusion will be displayed in a Consort diagram. Differences in proportions between baseline characteristics and outcome will be tested by Fisher exact test. Differences in mean or medians between the treatment groups will be tested by either Student's t-test or Mann Whitney U test depending on distribution. Normality assumptions will be assessed with Kolmogorov Smirnov – test. The estimated between group differences will be presented as proportions and 95% confidence intervals (CI), which will be calculated by the asymptotic method without continuity correction. P-values below 0,05 will be considered statistically significant. Main results will be reported as proportions.

In addition, comparisons between the treatment groups (CO-CPR vs CPR) with respect to the outcomes will be adjusted for background characteristics factors through Binary logistic regression to adjust for possible imbalances due to randomization between the treatment groups. The association between treatment and primary outcome will be presented as odds ratios and corresponding 95% CI intervals. Statisticians at Karolinska Institutet will be responsible for the statistical analysis.

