#### **6.4.3 Exploratory outcomes:**

- VT/VF as first rhythm
- Return of spontaneous circulation (ROSC)
- Repeated analysis of primary endpoint and all secondary endpoints at 24 months

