### 10.2 Statistical hypothesis for non-inferiority

#### 10.2.1 Null hypothesis:

The percentage in 30-day survival for those on the standard treatment instruction CPR is better (higher) than the percentage for those on instruction CO-CPR by an amount of 1.0-percentage units.

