### CONSORT 2010 Flow Diagram

## **10.6 Non-Inferiority and Superiority testing**

First, the primary analysis will be performed for non-inferiority in the PP1 population. If the primary analysis rejects the null hypothesis (i.e. CO-CPR is non-inferior to CPR with respect to the primary or some secondary outcomes), the comparisons between the treatment groups will also be done for superiority using 95% two sided confidence interval.(28) Second, the same analysis (first non-inferiority and then superiority) as above will be done for the ITT and PP2 population. The non-inferiority limit 1% will be used for both primary and secondary outcomes.

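### The covariate-adjusted analysis of 30-day survival is planned only as an odds ratio, so it cannot be read directly against the 1.0-point non-inferiority limit

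*Combined protocol and SAP*

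**What the plan says.** The decision scale is absolute throughout. Section 10.1 states: "The largest difference in 30-day survival (primary outcome) that is considered clinically relevant is 1.0 percentage point". The null hypothesis in Section 10.2.1 is that survival under standard CPR is "better (higher) than the percentage for those on instruction CO-CPR by an amount of 1.0-percentage units". Section 10.6 adds: "The non-inferiority limit 1% will be used for both primary and secondary outcomes". The main comparison is on the same scale: Section 10.1 plans a large-sample 95% confidence interval for the between-group difference and says "Main results will be reported as proportions".

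Section 10.1 then adds a second analysis, in which the comparisons are "adjusted for background characteristics factors through Binary logistic regression". Its stated purpose is to deal with chance imbalance between the arms. Its result for the primary outcome is specified as follows: "The association between treatment and primary outcome will be presented as odds ratios and corresponding 95% CI intervals".

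Four things are not stated anywhere: a margin on the odds-ratio scale, a conversion of the adjusted result to a risk difference, the covariates, and the population in which the adjusted model is fitted. Section 10.6, which sets the testing sequence (PP1 first, then ITT and PP2), does not mention the adjusted model.

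**The concern.** The primary question is whether CO-CPR loses more than 1.0 point of 30-day survival. An adjusted odds ratio with its interval does not answer that by itself. The odds ratio that corresponds to a 1.0-point loss moves with control survival, and a logistic odds ratio is conditional on the covariates in the model.

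This trial has a particular reason to want a readable adjusted result. PP1 keeps only patients whose bystanders received the allocated instruction, as judged by call audit (Section 10.4), and Section 10.5 expects 20% not to receive it. That selection happens after randomisation. If one instruction is harder to deliver in certain kinds of call, the PP1 arms may differ in more than chance. The adjusted model is the plan's only covariate-based check on this. It can deal only with measured covariates, but it should at least show whether the non-inferiority conclusion survives them.

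The covariates are also open. The register variables in Section 8 list first recorded rhythm beside age, sex and location. Section 6.4.3 makes "VT/VF as first rhythm" an exploratory outcome, and it is recorded after the instructions begin. Adjusting for it could remove part of the treatment effect, which in a non-inferiority comparison could hide harm.

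**Working it through.** **Inputs from the documents.** Margin 1.0 point (Sections 10.1, 10.2, 10.5, 10.6). Survival 11% for S-CPR and 13.1% for CO-CPR, one-sided alpha 2.5%, power 80%, 1630 per arm in PP1 (Section 10.5). Overall Swedish survival of 10-12% (Section 9.3), used here as a range for control survival.

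**Assumption.** The share of outcome variance explained by baseline covariates (R²) is not in the documents. Values from 0 to 20% are shown.

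**1. The plan's own figure.** Unpooled formula:

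- Variance term: 0.11 × 0.89 + 0.131 × 0.869 = 0.2117.
- n per arm = 0.2117 × (1.960 + 0.842)² / (0.021 + 0.010)² = 1730, against 1630 in the plan.
- At 1630 per arm: SE = √(0.2117/1630) = 1.14 points, and power = Φ(0.031/0.0114 − 1.960) = 77.6%.

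Pooled variance gives 1732 and Farrington-Manning 1736. Some less usual variants come near 1630; for example, using the control-arm variance in both arms gives 1600. This is a separate matter. It is used here only as the starting point for step 4.

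**2. The odds ratio equal to a 1.0-point loss.** OR = [(p − 0.01)/(1 − p + 0.01)] / [p/(1 − p)], where p is control survival.

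| Control survival | OR equal to a 1.0-point loss | Loss allowed by a fixed OR of 0.899 |
|---|---|---|
| 10% | 0.890 | 0.92 points |
| 11% | 0.899 | 1.00 points |
| 12% | 0.906 | 1.08 points |

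Outside the documents' range the drift is larger: OR 0.866 at 8% and 0.922 at 15%.

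Using the control survival seen in the trial does not remove the problem. With 1630 controls at 11%, its SE is √(0.0979/1630) = 0.775 points, so its 95% CI is about 9.5% to 12.5%. The same formula then gives limits from 0.885 to 0.910.

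**3. Conditional against marginal odds ratio.** Simulation: 1630 per arm and one binary covariate with 30% prevalence (assumed). Under 11% vs 13.1% the marginal OR is 1.22. The conditional OR is 1.23, 1.25 and 1.27 for covariate ORs of 2.7, 7.4 and 12.2. With truth exactly at the margin (11% vs 10%) and a covariate OR of 7.4, the marginal OR is 0.899 and the conditional OR 0.889. So even with control survival known, the limit in step 2 would not be the right one for the adjusted model.

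**4. What standardisation would give.** A standardised risk difference from the same model is on the margin's scale. Its variance is approximated by multiplying the unadjusted variance by (1 − R²), at 1630 per arm and 11% vs 13.1%:

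| R² (assumed) | SE (points) | Power |
|---|---|---|
| 0 | 1.14 | 77.6% |
| 2.7% | 1.12 | 78.7% |
| 5% | 1.11 | 79.7% |
| 10% | 1.08 | 81.8% |
| 20% | 1.02 | 86.0% |

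In the simulation, a variance reduction near 20% needed a covariate OR of 12.2. Nothing in the documents suggests that age, sex or location is that strong, so 3-10% is the range used below. In 1500 simulated trials at the margin (covariate OR 7.4), the one-sided error was 2.7% for both the unadjusted and the standardised analysis.

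**The case against.** The strongest reply is that the confirmatory test is sound and that the adjusted model is blamed for not doing a job it was never given. The margin, the hypotheses and the main result share one scale, and Section 10.6 gives the adjusted model no part in testing. Its stated purpose is imbalance, not precision. This stands. A reader might infer that the primary non-inferiority test is invalid, but the documents do not support that.

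A reader might also infer that the adjusted analysis is uninformative. That goes too far. An adjusted odds ratio can be set beside a crude one, and for the superiority step the null is an odds ratio of 1, which needs no margin. Within 10-12% control survival the limit moves only from 0.890 to 0.906, so a rough reading is possible. What remains is that a rough reading is not a decision rule, and that checking imbalance in a non-inferiority trial itself calls for a result that can be held against the margin.

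On first rhythm, the plan does not say that it will be adjusted for. The reference to background characteristics and to imbalance from randomisation points to pre-randomisation factors, and listing initial rhythm as a subgroup variable in Section 10.7 does not make it a covariate. The documents support only the narrower criticism: the covariates are unnamed, so the wording leaves first rhythm possible.

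Finally, the adjusted risk difference could be urged as the new primary estimate for its precision. The gain rests on an assumed R² and on the favourable 13.1% scenario; at equal survival of 11%, power is about 15% with or without it (14.7% at R² 0, 15.9% at R² 10%). Replacing the primary analysis after an interim review that included 30-day survival (Section 11) is debatable, and it is not needed.

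**Conclusion.** The point holds for a supporting analysis. The unadjusted primary test is valid and correctly scaled. The adjusted analysis of the primary outcome is planned only as a conditional odds ratio, with no odds-ratio margin and no conversion, so it cannot be read directly against the 1.0-point limit. The corresponding odds ratio runs from 0.890 to 0.906 over the documents' own 10-12% survival range, before allowing for the conditional scale. This is worth correcting because PP1 is selected after randomisation and the adjusted result is the plan's check against measured imbalance.

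The precision gain is secondary: about 1 to 4 points of power, from 77.6% at the planning rates, for an assumed R² of 3-10%. The case for the change does not depend on it.

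**What to change.** Keep the unadjusted difference in PP1 as the primary analysis, and keep the adjusted odds ratio. Add to Section 10.1, with a cross-reference in Section 10.6:

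- From the same logistic model, report the standardised (g-computation) risk difference with a 95% CI, and compare its lower bound with -1.0 point. Make this a pre-specified supporting analysis in PP1 and ITT, and state the variance method.
- Name the covariates and restrict them to pre-randomisation variables: age, sex, location of arrest, and period before or after the 2020-2022 pause. The first three and the date of arrest are already collected (Section 8).
- State that first recorded rhythm and other variables arising after randomisation are not adjusted for.

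Fix the wording in a dated SAP amendment before the allocation code is broken. The cost is that amendment and a little extra analysis in R, which Section 10.3 already specifies. No patients or new data are needed.

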### 10.2 Statistical hypothesis for non-inferiority

#### 10.2.1 Null hypothesis:

The percentage in 30-day survival for those on the standard treatment instruction CPR is better (higher) than the percentage for those on instruction CO-CPR by an amount of 1.0-percentage units.

#### 10.2.2 Alternative hypothesis:

The percentage in 30-day survival for those on instruction CO-CPR is better than the standard treatment instruction CPR or only slightly worse (by no more than 1.0 percentage unit). We will call instruction of CO-CPR non-inferior to instruction of S-CPR with respect to 30-day survival if the null hypothesis is rejected.

### 10.3 General statistical methods

All statistical analyses will be performed using IBM SPSS version 25 and R version 3.3.0 or higher. Patient data listings, summary tables and graphical presentations will be provided as applicable. For continuous variables, descriptive statistics such as mean, standard deviation, median and range will be presented. For discrete variables, counts and percentages will be presented.

Unless otherwise stated, all statistical tests will be performed at the 5 % two-sided alpha significance level.

## 10.4 Analysis step and strategy of the whole study populations

The target study population is witnessed OHCA of medical origin where any bystander at the scene has previous CPR training. All randomized calls of suspected OHCA will be included.

Patient with previous decision that CPR should not be initiated i.e. terminal illness or palliative care and cases where EMS did not start CPR for other reasons (sure signs of death, not true OHCA) will be excluded from data analysis. The remaining patients will be analyzed in the ITT population.

Blinded call audit will be used to define type of CPR instructions provided. All randomized EMS treated OHCA receiving instructions in accordance with randomized allocation will be treated as the target study population treated per protocol (PP1).

Finally, patients who are randomized but later judged as not fulfilling all criteria for inclusion before randomization, as evaluated by call audit (not witnessed, asphyxic, bystanders with no previous CPR training), will be removed and remaining patients will be analyzed as PP2.

Thus, we perform ITT analysis, PP1 and PP2 analysis based on the following patients:

Intention to treat (ITT) analysis: We define the ITT population as all included and randomized EMS treated OHCA patients that not fulfilled any exclusion criteria's.

Per protocol 1 (PP1): We define the PP population as the subset of the ITT population where the bystanders received the allocated instructions by the dispatch operator, as defined by the call audit.

Per protocol 2 (PP2): We define the PP2 population as the subset of the PP1 population where the patients fulfilled all inclusion criteria, as defined by call audit.

Please see also Consort Diagram in section 10.5.

The reasoning behind excluding patients after randomization is two-folded:

First: Dispatchers suspecting OHCA based on initial information in a phone-call do patient inclusion and randomization. In this situation there is very limited information and dispatchers are encouraged to treat all calls where the patients are not conscious and not breathing normally as suspected OHCA

and start CPR instructions. Therefore, patients who do not have a treatable OHCA might be included and randomized. These patients can be divided in two categories, either it's not a true OHCA (the patient never suffered an OHCA, for example fainted and thus has a pulse at EMS arrival) or the patients is already dead or had a previous decision that CPR should not be initiated. Therefore, EMS treated OHCA will serve as the best possible evaluation of treatable OHCA.

Second: The reason for including all randomized EMS treated OHCA is because at the time of randomization the dispatch operator judges the call as meeting all inclusion criteria and no exclusion criteria. If call audit or EMS record later reveal that the OHCA was not witnessed, traumatic, caused by asphyxia or bystanders without previous CPR training, the initial selection still relied on the dispatcher. Therefore, further removal of patients in the PP1 analysis might interfere with the interpretation of the study intervention in a real-life setting. A secondary analysis will be performed in all patient fulfilling all inclusion (PP2).

[figure not shown]

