### 5.3: Post randomization exclusion from data analysis:

- Previous decision that CPR should not be initiated *i.e.* terminal illness or palliative care
- No cardiac arrest, other condition (cases where EMS did not start CPR)

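### 'EMS treated OHCA' is defined differently in Sections 5.3/10.4 and Section 8, so ITT and PP1 membership is unclear for AED-shocked patients and for arrests reversed by bystander CPR alone

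*Combined protocol and SAP*

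**What the plan says.** Three places in the combined protocol and SAP decide who is analysed.

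- **Section 5.3** lists a post-randomisation exclusion worded "No cardiac arrest, other condition (cases where EMS did not start CPR" and closes the bracket there.
- **Section 10.4** states that "cases where EMS did not start CPR for other reasons (sure signs of death, not true OHCA) will be excluded from data analysis". It then defines the widest set: "We define the ITT population as all included and randomized EMS treated OHCA patients", with no exclusion criterion met. PP1, the primary set, is a subset of ITT, and PP2 is a subset of PP1.
- **Section 8** (SCAR variables) says "In calls where there is no matching report in SCAR, ambulance records will be reviewed", and that "if EMS has performed CPR or the patient had been defibrillated by an AED the case will be classified as" EMS treated. For the other calls it says only "For all EMS treated OHCA the following variables will be collected from the Swedish Cardiac Arrest Register", without saying what makes a matched case EMS treated.

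Section 10.4 explains the exclusions by two kinds of patient: those with no true arrest ("the patient never suffered an OHCA, for example fainted and thus has a pulse at EMS arrival"), and those already dead or with a prior decision against CPR. It concludes that "EMS treated OHCA will serve as the best possible evaluation of treatable OHCA". Under Section 6.2.2 the intervention ends when EMS or first responders arrive.

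**The concern.** Two groups are affected.

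1. Patients shocked by an AED who needed no CPR from EMS. Section 8 keeps them; the wording of 5.3 and 10.4 removes them.
2. True arrests in which bystander CPR alone restored a pulse, with no shock and no EMS CPR. The wording of 5.3 removes them, and so does Section 8 for unmatched calls. Yet they had an arrest, were not dead and had no prior decision against CPR, so no reason given in the text covers them.

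Most post-randomisation exclusions here concern facts fixed before the call. This one is different: the need for EMS CPR is observed once the allocated instructions have had their whole effect, and it may depend on them. The excluded patients would also be among the likelier survivors. Because the sets are nested, a patient who leaves ITT cannot return in PP1 or PP2. More losses from S-CPR would favour declaring CO-CPR non-inferior; more losses from CO-CPR would be conservative and cost power.

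**Working it through.** **Membership under each passage**

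| Patient | 5.3 wording | 10.4 | Section 8, no SCAR match | SCAR-matched |
|---|---|---|---|---|
| AED shock, no EMS CPR | out | out, unless only the bracketed reasons count | in | no criterion stated |
| Pulse regained by bystander CPR alone | out | out, unless only the bracketed reasons count | out | no criterion stated |

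The first row is a direct conflict. The second is an exclusion without a matching reason on one reading and an inclusion on another.

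**The plan's own figures.** Section 10.5 assumes 11% (S-CPR) and 13.1% (CO-CPR) survival, a 1.0-point margin, one-sided alpha 2.5%, 1630 per arm in PP1, 20% not receiving the allocated instruction and 40% excluded.
- Recruitment: 3260/(0.8 × 0.6) = 6791.7, rounded up to 6792, as stated.
- PP1 size: 1592 per arm with the null variance taken at 11% and 10%, or 1730 with the unpooled variance. The stated 1630 lies between these and is not disputed.
- Expected exclusions: 0.4 × 6792 = 2717. Expected ITT: 0.6 × 6792 = 4075, or 2038 per arm.
- One point of survival in PP1: 0.01 × 1630 = 16.3 survivors per arm.

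**Illustration of size.** The documents give neither the frequency nor the survival of the patients who might be dropped. Assume a fraction f of an arm's arrests is dropped and that these patients have survival s = 60% (range 40–80%). An arm with true survival p then shows

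(p − s·f)/(1 − f).

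Take true survival at the margin, 10% for CO-CPR and 11% for S-CPR, with 1630 analysed per arm. Use the unpooled standard error and claim non-inferiority if the lower 95% limit exceeds −1.0 point. For losses of 1% (CO-CPR) and 2% (S-CPR):
- CO-CPR: (0.10 − 0.6 × 0.01)/0.99 = 9.495%
- S-CPR: (0.11 − 0.6 × 0.02)/0.98 = 10.000%
- Difference −0.505 point, a shift of about +0.5; SE 1.039 points
- One-sided type I error Φ((−0.505 + 1.0)/1.039 − 1.96) = 6.9%

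| Lost, CO-CPR / S-CPR | Shift in points (s = 40–80%) | One-sided type I error (s = 40–80%) |
|---|---|---|
| 2% / 2% | −0.02 | 2.4% |
| 1.0% / 1.2% | +0.09 (0.05 to 0.13) | 3.0% (2.8–3.3%) |
| 1.0% / 1.5% | +0.24 (0.14 to 0.34) | 4.2% (3.4–5.2%) |
| 1% / 2% | +0.50 (0.3 to 0.7) | 6.9% (4.6–10.1%) |
| 1.2% / 1.0% | −0.11 | 1.9% |
| 2% / 1% | −0.53 | 0.7% |

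At the design rates of 13.1% and 11%, equal 2% losses shift the difference by +0.04 point. Losses of 2% (CO-CPR) and 1% (S-CPR) lower power from 77.6% to 66.2% by the same approximation.

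In patients, 1% against 2% of 2038 is about 20 against 41; 1.0% against 1.2% is about 20 against 24, a gap too small for counts alone to reveal.

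**The case against.** The strongest reply is that this is loose drafting. The 5.3 item is labelled as no cardiac arrest, which an AED-shocked arrest plainly is not, and Section 8 can be taken as the working rule for the ITT term. Section 10.4 can be read as excluding only the reasons in its brackets, with everyone else staying in ITT. A SCAR record might itself count as proof of EMS treatment. The CONSORT diagram to which 10.4 refers was not in the text available for this review and may list further reasons.

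Much of this stands. A reader might infer that bystander-only resuscitations are certainly lost from all three sets. The documents do not establish that: matched calls have no stated criterion, and the narrow reading of 10.4 would keep these patients. A reader might also infer that a pulse at EMS arrival is the plan's test for no arrest. It is not: the pulse is given as a consequence of fainting. What remains is that 5.3, 8 and 10.4 allow different analysis sets, and nothing says which governs.

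Objections to the remedy also have force. Every randomised caller is told to give compressions, so compressions heard on the call do not separate arrest from fainting. If 1–5% of the 2717 exclusions were wrongly admitted (an assumption), 27–136 non-arrests would enter, against about 44–61 true cases under the unequal-loss scenarios above (20 + 24 to 20 + 41). A −1.0-point difference would be diluted to between −0.99 (4075/4102) and −0.97 (4075/4211). If all 136 survived, overall survival from an 11% base would rise to about 13.9% and the standard error by about 9%. These are reasons to keep the analysis supportive and its entry criterion strict.

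**Conclusion.** The concern holds as an unresolved definition. AED-shocked patients without EMS CPR are classified in contradictory ways, and the status of arrests reversed by bystander CPR alone is ambiguous. Because the deciding event follows the intervention, the ambiguity bears on possible bias as well as on wording.

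Its size is unknown. The type I error figures rest wholly on assumed loss rates, assumed survival and an assumed imbalance between arms, and they suppose that every such patient is dropped. A reader might infer from the 6.9% that the trial's error rate is inflated. The documents do not support that: they give no frequency and no direction, equal or nearly equal losses matter little, and about half the margin is reached only with a marked imbalance such as 1% against 2%. That scenario would remove about 11% of S-CPR survivors (0.02 × 0.6/0.11). The point should be settled before unblinding because it is cheap to settle and the margin is narrow. It does not show that the primary analysis is wrong.

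**What to change.** Before unblinding:

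1. Reconcile Sections 5.3, 8 and 10.4 into one definition of EMS treated OHCA. It should include the AED criterion of Section 8 and be applied blind to allocation, in the same way, to SCAR-matched and unmatched calls. Leave the primary set otherwise unchanged.
2. Report post-randomisation exclusions by arm and by reason, with a separate count of arrests in which a pulse was regained before EMS arrival.
3. Add a supportive sensitivity analysis of 30-day survival that includes those arrests. Entry should need a pre-stated criterion, judged blind, that the EMS or hospital record documents a cardiac arrest; compressions confirmed on the call are not enough.
4. State where survival comes from for these patients, for example the population-register linkage. No source is given for unmatched cases not classed as EMS treated.

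**Cost.** Wording changes and one further analysis. Ambulance-record review of unmatched calls (Section 8), blinding during data collection (8.1) and a CONSORT display (10.1) are already planned. Some extra record and call review is needed, because the audit in Section 8 covers only EMS-treated calls. Some non-arrests may enter, but only in the sensitivity analysis.
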